## **CONFIDENTIAL PROTOCOL**

An Open Label, Safety Study to Assess the Potential for Adrenal Suppression Following Treatment with Desoximetasone 0.15% Topical Spray (Taro Pharmaceuticals U.S.A., Inc.) in Patients with Atopic Dermatitis

---

**CONFIDENTIAL PROTOCOL**

An Open Label, Safety Study to Assess the Potential for Adrenal Suppression Following Treatment with Desoximetasone 0.15% Topical Spray (Taro Pharmaceuticals U.S.A., Inc.) in Patients with Atopic Dermatitis

**CONFIDENTIAL PROTOCOL**

An Open Label, Safety Study to Assess the Potential for Adrenal Suppression Following Treatment with Desoximetasone 0.15% Topical Spray (Taro Pharmaceuticals U.S.A., Inc.) in Patients with Atopic Dermatitis

---

## **CONFIDENTIAL PROTOCOL**

An Open Label, Safety Study to Assess the Potential for Adrenal Suppression Following Treatment with  
Desoximetasone 0.15% Topical Spray (Taro Pharmaceuticals U.S.A., Inc.) in Patients with Atopic Dermatitis

---

**CONFIDENTIAL PROTOCOL**

An Open Label, Safety Study to Assess the Potential for Adrenal Suppression Following Treatment with Desoximetasone 0.15% Topical Spray (Taro Pharmaceuticals U.S.A., Inc.) in Patients with Atopic Dermatitis

**4.0 SYNOPSIS**

Protocol Number	DSXS 1502a
Title	An Open Label, Safety Study to Assess the Potential for Adrenal Suppression Following Treatment with Desoximetasone 0.15% Topical Spray (Taro Pharmaceuticals U.S.A., Inc.) in Patients with Atopic Dermatitis
Objectives	

1. The objective of this study is to evaluate the potential of desoximetasone 0.15% topical spray to suppress HPA axis function in patients with moderate to severe atopic dermatitis.

2. The secondary objectives are to evaluate the efficacy parameters and adverse event (AE) profiles of desoximetasone 0.15% topical spray administered to patients with moderate to severe atopic dermatitis.

Sponsor	Taro Pharmaceuticals U.S.A., Inc.
Name of Test Product	Desoximetasone 0.15% Topical Spray
Route of Administration	Topical
Study Design	An open label, safety study to assess the potential for adrenal suppression following treatment with desoximetasone 0.15% topical spray administered twice daily for 28 days in patients with moderate to severe atopic dermatitis
Study Population	Approximately twenty-five (25) to fifty (50) patients stratified by age with a confirmed diagnosis of moderate to severe atopic dermatitis with: Cohort 1 – 10-20 patients age 12-17 years of age with 10-30% body surface area (BSA) affected Cohort 2 – 5-10 patients age 6-11 years of age with 10-30% body surface area (BSA) affected Cohort 3 – 5-10 patients age 2-5 years of age with 10-30% body surface area (BSA) affected Cohort 4 – 5-10 patients 6 months- 1 year of age with 10-30% body surface area (BSA) affected  Cohorts will be enrolled in sequential order. Each cohort will initiate enrollment once the previous cohort has reached the minimum number of patients and a safety analysis has been reviewed. Each cohort will be enrolled based on the availability of patients.  Each cohort will be reviewed for the potential of HPA axis suppression. If at

**CONFIDENTIAL PROTOCOL**

An Open Label, Safety Study to Assess the Potential for Adrenal Suppression Following Treatment with Desoximetasone 0.15% Topical Spray (Taro Pharmaceuticals U.S.A., Inc.) in Patients with Atopic Dermatitis

	
least 50% of patients in each Cohort experience HPA axis suppression once the minimum number of patients has been enrolled and completed the cohort, enrollment for that cohort will be stopped and no further cohorts will be initiated. If at least 35% of patients have experienced HPA axis suppression across cohorts combined during the study, enrollment will be discontinued and no other cohorts will be initiated. Cohort 2 will not begin until safety data has been reviewed for Cohort 1. The same process will be followed for each Cohort until the study is complete.
 
The enrollment in the individual Cohort may not require if the satisfactory safety data for the same age group was obtained in the study DSXS 1502.

Study Conduct	
All patients will attend the clinic for 3 scheduled visits:
 
Visit 1: Screening/Enrollment (Day 1)
 
Visit 2: Interim Visit (Day 14 ± 2)
 
Visit 3: End of Study (Day 29 ± 2) or Early Termination

Inclusion Criteria	

1. Male or non-pregnant, non-lactating females:

• Cohort 1 –ages 12-17 years of age

• Cohort 2 –ages 6-11 years of age

• Cohort 3 –ages 2-5 years of age

• Cohort 4 – patients 6 months - 1 year of age

2. If female and of child-bearing potential, prepared to abstain from sexual intercourse or use a reliable method of contraception during the study (e.g., condom, IUD, oral, transdermal or injected hormonal contraceptives)

3. Parent/legal guardian has signed informed consent form, which meets all criteria of current FDA regulations.

4. Based on the patient's age, 11 -17 year olds will read and sign an IRB approved assent form. Patients 6-10 years of age will provide verbal assent to participate.

5. Patients with a definite clinical diagnosis of stable atopic dermatitis with involvement of:

• Cohort 1 –age 12-17 years of age with 10-30% body surface area (BSA) affected (excluding face, axilla and groin areas)

• Cohort 2 – age 6-11 years of age with 10-30% body surface area (BSA) affected (excluding face, axilla and groin areas)

• Cohort 3 –age 2-5 years of age with with 10-30% body surface area (BSA) affected (excluding face, axilla and groin areas)

• Cohort 4 – 6 months - 1 year of age with 10-30% body surface area (BSA) affected (excluding face, axilla and groin areas)

6. Have an Eczema Area and Severity Index (EASI) score of at least 15

7. Have an Investigator Global Assessment Scale (IGA) of 3 (Moderate) or 4 (Severe)

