## 9.0 INVESTIGATIONAL PLAN

### 9.1 Study Design and Plan Description

This open label, safety study is designed to evaluate the potential for adrenal suppression after treatment with desoximetasone 0.15% topical spray (Taro Pharmaceuticals, U.S.A.), for the treatment of moderate to severe atopic dermatitis.

Approximately 25 to 50 eligible patients with atopic dermatitis that satisfy all eligibility criteria will be enrolled into the study at Visit 1. Patients must be overall in good health. They should have a current diagnosis of moderate to severe atopic dermatitis with IGA score of at least 3 or 4.

Approximately twenty-five (25) to fifty (50) patients stratified by age with a confirmed diagnosis of moderate to severe atopic dermatitis with:

**Cohort 1** – 10 -20 patients age 12-17 years of age with 10-30% body surface area (BSA) affected

**Cohort 2** – 5-10 patients age 6-11 years of age with 10-30% body surface area (BSA) affected

**Cohort 3** – 5-10 patients age 2-5 years of age with 10-30% body surface area (BSA) affected

**Cohort 4** – 5-10 patients 6 months to 1 year of age with 10-30% body surface area (BSA) affected

Cohorts will be enrolled in sequential order. Each cohort will initiate enrollment once the previous cohort has reached the minimum number of patients and a safety analysis has been reviewed. Each cohort will be enrolled based on the availability of patients.

Each cohort will be reviewed for the potential of HPA axis suppression. If at least 50% of patients in a Cohort experience HPA axis suppression, enrollment for that cohort will be stopped and no further cohorts will be initiated. If at least 35% of patients have experienced HPA axis suppression across all cohorts combined during the study, enrollment will be discontinued and no

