## **CONFIDENTIAL PROTOCOL**

An Open Label, Safety Study to Assess the Potential for Adrenal Suppression Following Treatment with Desoximetasone 0.15% Topical Spray (Taro Pharmaceuticals U.S.A., Inc.) in Patients with Atopic Dermatitis

---

from a post-treatment cortisol response test will be included in the analysis. Patients who have not used 42 doses of the study drug will be excluded from the primary analysis of HPA axis suppression.

The primary analysis of interest is the proportion of patients in each group who are considered to have demonstrated possible HPA axis suppression following treatment with the study medication. As a secondary analysis of the data a logistic regression of the proportion of patients in the study with HPA axis suppression will be performed with %BSA affected as a covariate. See Appendix E for results from the cortisol response test considered indicative of potential HPA axis suppression.

The study will be enrolled by Cohort starting with Cohort 1 and each cohort will be reviewed for the potential of HPA axis suppression. If at least 50% of patients in Cohort 1 experience HPA axis suppression once the minimum number of patients has been enrolled and completed the cohort, enrollment for that cohort will be stopped and no further cohorts will be initiated. If at least 35% of patients have experienced HPA axis suppression across cohorts combined during the study, enrollment will be discontinued and no other cohorts will be initiated. Cohort 2 will not begin until safety data has been reviewed for Cohort 1. The same process will be followed for each Cohort until the study is complete.

For all patients the actual amount of desoximetasone (mg) applied during the study will be calculated from recorded bottle weights and presented.

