7.2 Safety Analysis of Potential HPA Axis Suppression

Dosing will be twice a day for 28 days excluding the doses prior to the Cortisol Response Test (54 applications). All patients who are enrolled, use at least 42 doses of the study drug and have data from a post-treatment cortisol response test will be included in the analysis. Patients who have not used 42 doses of the study drug will be excluded from the primary analysis of HPA axis suppression.

The primary analysis of interest is the proportion of patients in each group who are considered to have demonstrated possible HPA axis suppression following treatment with the study medication. As a secondary analysis of the data a logistic regression of the proportion of patients in the study with HPA axis suppression may be performed with %BSA affected as a covariate. This will depend on the distribution of the %BSA data collected.

The study will be enrolled by Cohort starting with Cohort 1 and each cohort will be reviewed for the potential of HPA axis suppression. If at least 50% of patients in Cohort 1 experience HPA axis suppression once the minimum number of patients has been enrolled and completed the cohort, enrollment for that cohort will be stopped and no further cohorts will be initiated. If at least 35% of patients have experienced HPA axis suppression across cohorts combined during the study, enrollment will be discontinued and no other cohorts will be initiated. Cohort 2 will not begin until safety data has been reviewed for Cohort 1. The same process will be followed for each Cohort until the study is complete.

For all patients the actual amount of desoximetasone (mg) applied during the study will be

NOVUM PHARMACEUTICAL RESEARCH SERVICES
STATISTICAL ANALYSIS PLAN

Desoximetasone 0.15% Topical Spray

Protocol / Study No. DSXS 1502a / 71615002

calculated from recorded bottle weights and presented.

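### Nothing holds enrolment at a cohort's minimum while end-of-treatment cortisol results are pending, and the denominator of the two stopping percentages is undefined

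*Protocol*

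**What the plan says.** The protocol synopsis sets Cohort 1 at "10-20 patients age 12-17 years of age" and Cohort 2 at "5-10 patients age 6-11 years of age"; Cohorts 3 and 4 have the same 5 to 10 range. A cohort may open only after the one before it has reached its minimum (protocol 9.4.3 and SAP section 4 say its required number) and its safety data have been reviewed. Within a cohort, the only statement on pace is "Each cohort will be enrolled based on the availability of patients".

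The 50% rule appears in two forms.

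- **With a condition.** The synopsis (Study Population) has "once the minimum number of patients has been enrolled and completed the cohort, enrollment for that cohort will be stopped". Protocol 10.1.3 has "If at least 50% of patients in Cohort 1 experience HPA axis suppression once the minimum number of patients has been enrolled and completed" and then extends the process to each cohort. SAP 7.2 follows 10.1.3.
- **Without a condition.** Protocol 9.1 has "If at least 50% of patients in a Cohort experience HPA axis suppression, enrollment for that cohort will be stopped". The synopsis (HPA Axis Evaluation), protocol 9.4.3 and SAP sections 3 and 4 also omit any minimum or completion requirement.

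The pooled rule is "If at least 35% of patients have experienced HPA axis suppression across cohorts combined during the study, enrollment will be discontinued". It has no minimum number in either document. For neither rule do the documents say whether the percentage is of enrolled, completed or tested patients. SAP 7.6 states that no interim analysis is planned, so the SAP gives no data cut or denominator for the cohort reviews.

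**The concern.** The two rules limit how many children start a regimen once it is seen to suppress the adrenal axis too often. The deciding result arrives about four weeks after a child's first dose. Every cohort's maximum is twice its minimum, so the optional places equal the minimum in number. If enrolment continues while the first 10 (or 5) children are still on treatment, some or all of the optional 10 (or 5) may already be dosed when the conditioned 50% rule is first read. Stopping enrolment in that cohort would then protect few further children, or none.

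The undefined denominator compounds this. Two people reviewing the same results could reach opposite decisions, depending on whether children without a result yet are counted.

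**Working it through.** **Inputs from the documents.** Cohort minimums 10, 5, 5, 5 and maximums 20, 10, 10, 10 (synopsis; protocol 9.1). Visit 3 at Day 29 ± 2. Thresholds 50% (cohort) and 35% (pooled). **Not in the documents, so assumed:** accrual rate, laboratory and review time, true suppression rate.

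**Step 1: the plan's own range.** 10 + 5 + 5 + 5 = 25 and 20 + 10 + 10 + 10 = 50, which reproduces the stated 25 to 50. (The 35 in protocol 10.1.1 and SAP section 5 equals neither sum and has no derivation; it is not used here.) Optional places: 20 − 10 = 10 in Cohort 1 and 10 − 5 = 5 in each of Cohorts 2 to 4.

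**Step 2: the lag.** From Day 1 to Day 27 is 26 days; from Day 1 to Day 31 is 30 days. The conditioned rule therefore cannot be read until 26 to 30 days after the last of the minimum patients starts, plus laboratory time. With up to a week assumed for laboratory and review, the lag is 26 to 37 days.

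**Step 3: accrual that fills the cohort by that Visit 3.** Rate per week = 7 × (maximum − minimum) / lag.

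- Cohort 1: 70/30 = 2.333 to 70/26 = 2.692.
- Cohorts 2 to 4: 35/30 = 1.167 to 35/26 = 1.346.

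Laboratory time lowers these rates: at 37 days they are 70/37 = 1.89 and 35/37 = 0.95. At slower accrual over a nominal four weeks, 0.5 a week adds 2 children and 1 a week adds 4. At 2 a week, Cohort 1 gains 8 and a younger cohort fills its 5 places.

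**Step 4: what the denominator does.** Suppose the cohort has filled and only the minimum has been tested. For Cohort 1 (10 tested, 20 enrolled), the 50% rule needs 5 suppressed on a tested denominator, and 10 on an enrolled one, which is every child tested. The 35% rule needs 4 (0.35 × 10 = 3.5, rounded up) or 7 (0.35 × 20). For Cohorts 2 to 4 (5 tested, 10 enrolled), the 50% rule needs 3 or 5.

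As an example, 5 of 10 is 50%, but 5/20 = 25%, below both thresholds. In a younger cohort, 3 of 5 is 60%, but 3/10 = 30%.

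The chance of tripping is the binomial tail P(X ≥ r) with n = 10 or 5 tested. At an assumed true rate of 0.5:

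- Cohort 1, 50% rule: 638/1024 = 0.623 (tested) against 1/1024 = 0.001 (enrolled).
- Cohort 1, 35% rule: 848/1024 = 0.828 against 176/1024 = 0.172.
- Cohorts 2 to 4, 50% rule: 16/32 = 0.500 against 1/32 = 0.031.

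Over a range of assumed true rates (tested / enrolled denominator):

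| Rule | 0.35 | 0.50 | 0.70 |
|---|---|---|---|
| Cohort 1, 50% rule | 0.249 / <0.001 | 0.623 / 0.001 | 0.953 / 0.028 |
| Cohort 1 data alone, 35% rule | 0.486 / 0.026 | 0.828 / 0.172 | 0.989 / 0.650 |
| Cohorts 2–4, 50% rule | 0.235 / 0.005 | 0.500 / 0.031 | 0.837 / 0.168 |

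On a tested denominator there is no dilution. On that reading the unconditioned form has a different weakness: with no minimum, one suppressed child out of one tested is 100% and would trip it.

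**The case against.** A reader might infer three stronger things, and the documents do not support them.

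- **That untested children do dilute the percentage.** No passage says so. SAP section 7 computes categorical percentages on non-missing data. Protocol 10.1.3 and SAP 7.2 admit to the HPA analysis only patients with a post-treatment test. The conditioned rule speaks of patients who have completed. These fit a tested denominator at least as well, and an enrolled denominator that needs 10 of 10 suppressed is an unlikely intent. But none of them is tied to the cohort review, so the denominator remains undefined.
- **That this is the trial's only protection.** It is not. A younger cohort cannot open until the previous cohort's data are reviewed. Protocol 9.3.4 lets the investigator withdraw a patient to protect health and lists signs of possible suppression as a reason for early termination. The gap concerns the optional children of a cohort already open.
- **That nothing can act before the minimum completes.** The pooled 35% rule and the unconditioned 50% rule could. At about 2.4 enrolments a week, some 9.6 children enrol in four weeks, so about 5 have reached Visit 3 when the 15th enrols. However, no passage schedules a review at that point, and the conditioned form in the synopsis, 10.1.3 and SAP 7.2 still makes the 50% rule wait.

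It is also fair to say that accrual may be slow, in which case only a few extra children start. A further practical objection stands: under protocol 9.3.4 withdrawals are not replaced, so a pause that waits for a result from every one of the first 10 (or 5) could never lift after one loss. The fix must allow for that.

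**Conclusion.** The concern holds as a gap in the enrolment rule and an undefined denominator. Followed as written, the plan lets up to 10 optional children in Cohort 1, or 5 in each younger cohort, start treatment before the conditioned 50% rule can act. Filling the cohort by then rests on an assumed accrual of about 2.3 to 2.7 a week (Cohort 1) or 1.2 to 1.3 a week (Cohorts 2 to 4); at 0.5 to 1 a week the exposure is about 2 to 4 extra children. The loss of stopping probability, such as 0.62 to 0.001 for Cohort 1 at an assumed true rate of 50%, arises only if the cohort has filled and the percentage is taken over all enrolled. It is zero on a tested denominator. This should be fixed because the remedy is cheap; it is not an established numerical error.

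**What to change.** In the synopsis, protocol 9.1, 9.4.3 and 10.1.3, and SAP sections 3, 4 and 7.2, add:

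> Enrolment in a cohort pauses when its minimum has been enrolled and resumes only after review, which takes place when each of those patients has a post-treatment cortisol result or has left the study without one. At every review both percentages are computed over patients with a post-treatment cortisol result.

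Leave both thresholds unchanged. Reconcile the conditioned 50% rule (synopsis Study Population, protocol 10.1.3, SAP 7.2) with the unconditioned statements (synopsis HPA Axis Evaluation, protocol 9.1 and 9.4.3, SAP sections 3 and 4), so that one version stands and its completion wording agrees with the review trigger above.

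The cost is a short amendment and matching SAP text. Optional patients above the minimum start about four to five weeks later (26 to 37 days, allowing an assumed week for laboratory and review). The next cohort is not delayed, because it already waits for the same review.

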**CONFIDENTIAL PROTOCOL**

An Open Label, Safety Study to Assess the Potential for Adrenal Suppression Following Treatment with Desoximetasone 0.15% Topical Spray (Taro Pharmaceuticals U.S.A., Inc.) in Patients with Atopic Dermatitis

Exclusion Criteria	1. Females who are pregnant, nursing, planning to become pregnant during the duration of the study, or if of child-bearing potential and sexually active and not prepared to use appropriate contraceptive methods to avoid pregnancy 2. Lacks stable diagnosis of atopic dermatitis or has been diagnosed with mild atopic dermatitis 3. Have an EASI score of < 15. 4. Have an IGA score of < 3. 5. Atopic dermatitis with a BSA involvement of < 10% or < 30%. 6. Active cutaneous bacterial or viral infection in any treatment area at baseline (i.e., clinically infected atopic dermatitis) 7. Patient has a history of atopic dermatitis that has been unresponsive to topical corticosteroid therapy 8. Any condition (i.e., sunburn, psoriasis etc.) that, in the Investigator's opinion, may interfere with the clinical assessments of the signs and symptoms of atopic dermatitis 9. Patient has a history of allergy or sensitivity to corticosteroids or history of any drug hypersensitivity or intolerance which, in the opinion of the Investigator, would compromise the safety of the patient or the results of the study 10. Patient has a significant history or current evidence of chronic infectious disease, system disorder, organ disorder or other medical condition that, in the Investigator's opinion, would place the study patient at undue risk by participation in the study 11. Patient is currently receiving or has received any radiation therapy, anti-neoplastic agents or immunosuppressant medication within 4 weeks before the first dose of study drug 12. Use within one month before baseline of 1) oral or intravenous corticosteroids, 2) UVA/UVB therapy, 3) PUVA (psoralen plus ultraviolet A) therapy, 4) tanning booths, 5) nonprescription UV light source, 6) immunomodulators or immunosuppressive therapies, 7) interferon, 8) cytotoxic drugs, 9) tacrolimus or 10) pimecrolimus 13. Use within 14 days before baseline of 1) systemic antibiotics, 2) calcipotriene or other Vitamin D preparations, or 3) retinoids 14. Patients who have used topical treatments, prescription or over the counter, including: 

Any topical atopic dermatitis therapeutic agents of any kind within the 2 weeks before first use of study drug

Any topical corticosteroids within the 2 weeks before the first use of the study drug

Any antibacterial, medicated and/or astringent washes, soaps, pads or moisturizers within the 3 days before the first use of study drug.

High strength (20% or above) alpha-hydroxy acid or any kind of peel or other procedures on the face (e.g., laser hair removal) within 30 days of the study start

Any topical products (i.e., sunscreens, lotions, creams), except for

---------------------------	---

**CONFIDENTIAL PROTOCOL**

An Open Label, Safety Study to Assess the Potential for Adrenal Suppression Following Treatment with Desoximetasone 0.15% Topical Spray (Taro Pharmaceuticals U.S.A., Inc.) in Patients with Atopic Dermatitis

	
bland emollient (moisturizer) within 24 hour before baseline
 
f. Topical antibiotics in the treatment area within 7 days before baseline
 
15. Patient has been treated within 12 weeks (or five half lives, whichever is less) before the first dose of study drug with any biological therapies for atopic dermatitis
 
16. Use of non-sedating anti-histamines within the 7 days before the first dosing day
 
The use of sedating anti-histamines, such as diphenhydramine, may be acceptable on condition the patient has been on a stable dose for at least 14 days before the study start and will remain on a stable dose throughout the study
 
17. Any oral steroid drug use (with the exception contraceptives) within 28 days of the first dosing day or during the study
 

a. Female patients using hormonal contraceptives should have been on the same product/dosing regimen for at least 28 days before and should not change this regimen during the study

b. The use of inhaled or intranasal corticosteroids is acceptable as long as usage has been stable for at least 2 weeks before the first dose of study drug and will be continued during the study

 
18. Inability to understand the protocol requirements, instructions, and study-related restrictions, the nature, scope, and possible consequences of the clinical study.
 
19. Unlikely to comply with the protocol requirements, instructions, and study-related restrictions, such as uncooperative attitude, inability to return for follow-up visits, and improbability of completing the clinical study.
 
20. Receipt of any drug as part of a research study within 30 days prior to first dosing.
 
21. The patient is a member of the investigational study staff or a member of the family of the investigational study staff.
 
22. Previous participation in this study including patients previously enrolled in DSXS 1502.

Criteria for Evaluation	
Primary Outcome Measures: Hypothalamic Pituitary Adrenal (HPA) Axis Response to Cosyntropin demonstrating the absence or presence of adrenal suppression at the end of treatment
 
Secondary Outcome Measures: Hypothalamic Pituitary Adrenal (HPA) Axis Response to Cosyntropin demonstrating the presence of adrenal suppression at the end of treatment with % BSA as a covariate

